7.2.2 ELISA (IgG) ELISA Units for SARS-CoV-2

As the 2nd secondary objectives of demonstrating the noninferior immunogenicity of Novavax vaccine as a second (or subsequent) booster vs as a first booster of ancestral strain Novavax vaccine boost following mRNA vaccines, the derived/calculated endpoints of IgG response for **the group receiving ancestral strain Novavax vaccine** will include:

- IgG GMEU is calculated as the antilog of the mean of the log-transformed IgG GMEU. IgG GMEU will be summarized by visit day (Days 1 and 29) along with the corresponding 2-sided 95% CIs, by exponentiating the corresponding log-transformed means and their 95% CIs.
- GMFR_{Post/Pre} is calculated as the within-group ratio of post-vaccination IgG GMEU at Day 29 to pre-vaccination IgG GMEU at the baseline (Day 1). Similar sample SAS code as Nab will be applied to estimate IgG GMFR_{Post/Pre} and corresponding 95% CIs.
- GMR_{312/307} of IgG GMEU **28 days after a second (or subsequent) booster dose** of NVX-CoV2373 in Study **2019nCoV-312** versus **28 days after a first booster dose** of NVX-CoV2373 in Study **2019nCoV-307** among the same participants with corresponding 95% CIs will be conducted using paired t distribution. Non-inferiority will be demonstrated if GMR_{312/307} of IgG GMEU is higher than 0.67 and superiority will be demonstrated if GMR_{312/307} of IgG GMEU is higher than 1.0 after non-inferiority is successfully demonstrated.
- SCR is defined as proportion of participants who achieve seroconversion \geq 4-fold increase from baseline in IgG GMEUs at Day 29 if the baseline value is equal to or above LLOQ or at least 4-fold fold rise from LLOQ if the baseline value is lower than LLOQ. SCR in IgG GMEUs with corresponding two-sided exact binomial 95% CIs will be calculated using the Clopper-Pearson method.
- Two-sided 95% CIs of the difference in SCRs in IgG GMEU **28 days after a second (or subsequent) booster dose** of NVX-CoV2373 in Study **2019nCoV-312** relative to time of Day 1 dose in Study **2019nCoV-307** versus **28 days after a first booster dose** of NVX-CoV2373 in Study **2019nCoV-307** relative to time of Day 1 dose in Study **2019nCoV-307** among the same participants will be based on the method of confidence interval for the difference in two correlated proportions by Tango (SAP Section [11.6](#)). Non-inferiority will be demonstrated if the LB of the 95% exact CIs for the difference of SCRs (SCR₃₁₂ – SCR₃₀₇) in IgG GMEUs is higher than –10%.

As the 3rd secondary objectives of characterizing the cross-reaction of neutralizing and IgG antibodies induced by the ancestral strain Novavax vaccine to more recent SARS-CoV-2 variants and any other variants for which appropriate assays are available, the derived/calculated endpoints of IgG response for **the group receiving updated Novavax COVID-19 Vaccine based on recent variant(s)** will include IgG GMEU at Day 1 and Day 29, GMFR_{Post/Pre} (Day 29 vs. Day 1), GMR_{312/307}, SCRs (Day 29 vs. Day 1), and difference in SCRs (SCR₃₁₂ – SCR₃₀₇) in

IgG GMEU to be calculated using the same calculations and comparison periods as noted above for the group receiving ancestral strain Novavax vaccine.

Please note above parameters of IgG data (Wuhan) from both studies of Study 2019nCoV-307 and 2019nCoV-312 will be presented together and above parameters of IgG data (Omicron BA.5) from both studies will be presented together to evaluate the secondary endpoints.

7.2.3 hACE2 Receptor-binding Inhibition Titers for SARS-CoV-2

As the 4th secondary objectives of further characterizing antibody responses in a human angiotensin-converting enzyme 2 (hACE2) receptor binding inhibition assay to the SARS-CoV-2 ancestral strain spike protein, the derived/calculated endpoints of hACE2 response will include hACE2 GMTs at Day 1 and Day 29, GMFR_{Post/Pre} (Day 29 vs. Day 1), GMR_{312/307}, SCRs (Day 29 vs. Day 1), and difference in SCRs (SCR₃₁₂ – SCR₃₀₇) in hACE2 titers using the same calculations and comparison periods as noted above for neutralizing antibodies. Please note, SCR is defined as proportion of participants who achieve seroconversion \geq 4-fold increase from baseline in hACE2 titers at Day 29 if the baseline value is equal to or above LLOQ or at least 4-fold fold rise from LLOQ if the baseline value is lower than LLOQ.

Please note above parameters of hACE2 data (Wuhan) from Study 2019nCoV-307 will be presented together with the summary of 2019nCoV-312; hACE2 data (Omicron BA.5) of Study 2019nCoV-312 will be summarized including GMT, GMFR_{Post/Pre} and SCR.

7.3 Analyses of Secondary Endpoint of Safety

As the secondary objective of describing the overall safety of ancestral strain and updated (if administered) Novavax vaccine(s) administered as a second (or subsequent) booster following licensed mRNA vaccines and a first ancestral strain Novavax vaccine booster, safety data include Solicited AEs, unsolicited AEs through Day 29 after the vaccination dose, MAAEs and AESIs (including myocarditis and/or pericarditis) through Day 181 after the vaccine dose and SAEs Day 181 after the vaccine dose. All safety analyses will be descriptive and conducted using the Safety Analysis Set. Missing data will not be imputed.

7.3.1 Solicited Adverse Events

Solicited AEs for this study are pre-specified in Section 8 and Appendix 2 of the Study 312 Protocol, including both injection site reactions (ie, pain, tenderness, redness, and swelling) and systemic events (ie, fatigue, headache, myalgia, arthralgia, oral temperature [for assessment of fever], vomiting) that are reported within seven days following the Day 1 vaccination. These events are considered related to the test article and are collected using a severity rating of 0 (Normal), or 1, 2, or 3 (mild, moderate or severe, respectively), using the maximal severity observed for the specific symptom post-vaccination. Notable exceptions include oral temperature and events of injection site redness and swelling, which is collected as a continuous variable and that uses the grade ranges established in TGS (Table 10 in Appendix 3). Oral temperature (fever)

will be summarized by severity according to regulatory guidance, eg, Grade 0 (Normal) < 38.0°C, Grade 1 (Mild) = 38.0 – 38.4°C, Grade 2 (Moderate) = 38.5 – 38.9°C, Grade 3 (Severe) > 39.0 – 40 °C, Grade 4 (Potential Life Threatening) > 40. Redness/Swelling will be summarized by severity according to regulatory guidance, eg, Grade 0 (Normal) < 2.5 cm, Grade 1 (Mild) = 2.5 – 5 cm, Grade 2 (Moderate) = 5.1 – 10 cm, Grade 3 (Severe) > 10 cm. Extracts of solicited AEs of redness and swelling will be reviewed by the NVX clinical team and a final memo documenting the outcomes of the adjudication will be prepared by the NVX clinical team prior to database freeze (Day 29 primary analysis) or database lock (Final analysis). Any Grade 4 (Potential Life Threatening) solicited events will be provided to NVX Biostatistician team for analysis.

The number and percentage (with two-sided exact 95% CIs using the Clopper-Pearson method) of participants reporting solicited injection site and systemic AEs within the post-vaccination window (Days 1 – 7) by the verbatim terms, by severity (mild, moderate, severe, potentially life threatening) using the maximal severity observed for the specific symptom post-vaccination, or by day after vaccination and severity will be summarized for the study vaccine group. The number of participants with a solicited AE continuing beyond Day 7 will also be reported.

The duration of solicited local and systemic AEs within the 7 days after vaccination and beyond Day 7 will be summarized by the study vaccine group using several methods described below.

1. The number of days (count) that the reaction was reported within the 7-day reactogenicity period. For example, if fever was reported on Day 2, Day 3, and Day 5, then the count duration would be reported as 3 days.
2. The continuous duration of the event within the 7-day reactogenicity period. For example, if fever was reported on Day 2, Day 3, and Day 5, then the duration would be reported as 4 days using the date of Day 5 as ending date and date of Day 2 as the starting date of the event.
3. The continuous duration of the event including continuing reactions past the 7-day reactogenicity period. For example, if a Fever was reported on Day 3, Day 4, Day 6, and in a linked unsolicited AE with an end date of Day 8, then the duration would be reported as 6 days using the date of Day 3 as the starting date of the event.

The following summaries of all solicited AEs will be presented by the study vaccine group as the part of safety stated as the secondary endpoints:

- All local/systemic reactogenicity AEs by the verbatim terms within the post-vaccination window (Days 1 – 7)
- All local/systemic reactogenicity AEs by severity within the post-vaccination window (Days 1 – 7)
- All local/systemic reactogenicity AEs by the verbatim terms beyond 7 days following the study vaccine

- All local/systemic reactogenicity AEs by severity beyond 7 days following the study vaccine
- Duration of solicited TEAEs within the post-vaccination window (Days 1 – 7)
- Duration of all solicited TEAEs after Day 1
- Listings of participants with local/systemic reactogenicity AEs

7.3.2 Unsolicited Adverse Events

A MAAE is defined as an AE that leads to an unscheduled visit to a healthcare practitioner. All MAAEs will be reported from the time of study vaccination through Day 29. After Day 29, MAAEs attributed to study vaccine will be captured until EOS. AESIs include PIMMCs, myocarditis and/or pericarditis ([Table 11](#) in Appendix 4), and complications specific to COVID-19 ([Table 9](#) in Appendix 2). SAE is an event considered “serious” if, in the view of either the Investigator or Sponsor, it results in any of the outcomes listed in Section 8.1 of the Study 312 Protocol.

Unsolicited MAAEs through Day 29, and MAAEs attributed to study vaccine/AESIs/SAEs throughout the study will be summarized by the study vaccine group and by SOC/PT using the latest version of MedDRA, as well as by severity (Mild, Moderate, Severe) and relationship (not related, related) to the study vaccine to present the number and percentage with its corresponding exact 95% CIs using Clopper-Pearson method. For multiple occurrences of an AE in the same participant, a participant will be counted only once within an SOC or a PT, using the most severe occurrence and closest reported relationship for the summarization by severity or relationship to the study vaccine, respectively.

The duration of MAAEs through Day 29, MAAEs attributed to study vaccine after Day 29 until EoS, AESIs and SAEs throughout the study will be summarized and their corresponding by-participant listings will also be provided.

The following summaries of all unsolicited AEs will be presented by the study vaccine group as the part of safety stated as the secondary endpoints:

- Overall summary of all unsolicited TEAEs (Days 1 – 29)
- Summary of all unsolicited TEAEs by MedDRA SOC/PT and severity (Days 1 – 29)
- Summary of all unsolicited TEAEs by MedDRA SOC/PT and relationship to the study vaccine (Days 1 – 29)
- Summary of MAAEs by MedDRA SOC/PT and severity (Days 1 – 29)
- Summary of MAAEs by MedDRA SOC/PT and relationship to the study vaccine (Days 1 – 29)

- Summary of MAAEs attributed to study vaccine by MedDRA SOC/PT and severity (Days 1 – 29) and (Days 1 – 181)
- Summary of AESIs (including PIMMCs, myocarditis or pericarditis, and complications to COVID-19) by MedDRA SOC/PT and severity (Days 1 – 29) and (Days 1 – 181)
- Summary of AESIs (including PIMMCs, myocarditis or pericarditis, and complications to COVID-19) by MedDRA SOC/PT and relationship to study vaccine (Days 1 – 29) and (Days 1 – 181)
- Summary of SAE by MedDRA SOC/PT and severity (Days 1 – 29) and (Days 1 – 181)
- Summary of SAE by MedDRA SOC/PT and relationship to study vaccine (Days 1 – 29) and (Days 1 – 181)
- Duration of MAAEs (Days 1 – 29)
- Duration of MAAEs attributed to study vaccine (Days 1 – 29) and (Days 1 – 181)
- Duration of AESIs (Days 1 – 29) and (Days 1 – 181)
- Summary of unsolicited AEs leading to the discontinuation of study (Days 1 – 29) and (Days 1 – 181)
- Summary of SAEs leading to the discontinuation of study (Days 1 – 29) and (Days 1 – 181)
- Listings of all unsolicited AEs including MAAEs, AESIs (including PIMMCs, myocarditis or pericarditis and complications to COVID-19) and SAEs

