9. Reactogenicity (solicited adverse events related to vaccination) will be recorded by participants via diary on Days 1-7. The diary will be collected from the participant at the Day 8 visit and will be used to populate reactogenicity data in EDC. Should any reactogenicity event extend beyond 7 days after vaccination (toxicity grade  $\geq$ 1), then it will be recorded as an AE with the same start date as the reactogenicity event and followed to resolution.
10. All MAAEs and all AESIs (including potential immune-mediated medical conditions [PIMMCs] and myocarditis or pericarditis will be recorded. See [Table 3](#) for symptoms of myocarditis or pericarditis and [Table 4](#) for instructions for follow-up.
11. MAAEs attributed to study vaccine and all AESIs (including PIMMCs and myocarditis or pericarditis) will be recorded. See [Table 3](#) for symptoms of myocarditis or pericarditis and [Table 4](#) for instructions for follow-up.
12. EOS form will be completed for all participants, including participants who are terminated early.

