#### 8.1.4.3      **Medically Attended Adverse Events**

An MAAE is defined as an AE that leads to an unscheduled visit to a healthcare practitioner. All MAAEs will be reported from the time of study vaccination through Day 29. After Day 29, MAAEs attributed to study vaccine will be captured until EOS.

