#### 8.1.4.4 Reactogenicity Symptoms

On the day of vaccination, participants will remain in clinic (or under observation) for at least 15 minutes to be observed for any immediate reaction. Injection site specific local and general systemic reactogenicity reactions including start and stop dates will be recorded following vaccination. Any immediate reaction will be recorded as an AE on day of vaccination.

Participants will utilize their diary to record reactogenicity for the 7 days following vaccination. All participants will record reactogenicity starting on the same day of the vaccination and for a total of 7 days. Should any reactogenicity event extend beyond 7 days after vaccination (toxicity Grade  $\geq 1$ ), then it will be recorded as an AE with a start date that matches Day 8 of the reactogenicity event and followed to resolution per FDA guidelines for AE capture. The toxicity grading scale implemented in the diary is included in [Appendix 3](#).

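### SAP 7.3.2 has no rule to keep prolonged diary reactions out of the unsolicited TEAE tables, and its MAAE wording conflicts with the MAAE definition and endpoint

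*SAP*

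**What the plan says.** **Recording of prolonged reactions.** For a reaction of Grade 1 or higher that extends beyond 7 days, footnote 9 of Protocol Table 1 says: "then it will be recorded as an AE with the same start date as the reactogenicity event and followed to resolution". Protocol 6.1.3 and footnote 9 of SAP Table 7 give the same rule. Protocol 8.1.4.4 gives a different start: "then it will be recorded as an AE with a start date that matches Day 8 of the reactogenicity event".

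**Solicited tables.** SAP 7.3.1 gives an example of a fever reported on Days 3, 4 and 6 and "in a linked unsolicited AE with an end date of Day 8, then the duration would be reported as 6 days". The same section plans reactogenicity tables by term and by severity, for Days 1–7 and for the period beyond 7 days. It also plans a count of participants whose solicited event continues past Day 7.

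**Unsolicited tables.** SAP 7.3.2 opens its table list with "The following summaries of all unsolicited AEs will be presented by the study vaccine group". The first three items cover all unsolicited TEAEs for Days 1–29: an overall summary, a table by severity and a table by relationship. Nothing is said about linked records.

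**MAAEs.** Protocol 8.1.4.3 states: "An MAAE is defined as an AE that leads to an unscheduled visit to a healthcare practitioner". All MAAEs are collected through Day 29, and the secondary endpoint (Protocol Table 2, SAP Table 3) is not limited to unsolicited events. SAP 7.3.2, however, says: "Unsolicited MAAEs through Day 29, and MAAEs attributed to study vaccine/AESIs/SAEs throughout the study will be summarized". Protocol 9.3.3 uses the same qualifier. The MAAE table titles in SAP 7.3.2 omit it but stand under the unsolicited-AE header.

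**The concern.** Solicited and unsolicited events are reported separately so that expected reactogenicity does not cloud the search for unexpected events. If the continuation of a sore arm or a fever is also counted as an unsolicited TEAE, the unsolicited rate contains events already shown in the solicited tables. It no longer answers its own question. The related rate is affected too, wherever the investigator scores the continuation record as related.

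For MAAEs, the secondary endpoint asks how many participants had an AE that led them to seek care. If the tables are built from unsolicited records only, some vaccine reactions that led to a visit would be missing from that count. As the text stands, two programmers could produce different unsolicited and MAAE rates from the same data.

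**Working it through.** **1. The plan's own figures.** SAP 7.3.1 gives three worked durations, and all reproduce:
- Method 1, fever on Days 2, 3 and 5: a count of 3 days.
- Method 2, same days: 5 − 2 + 1 = 4 days.
- Method 3, fever from Day 3 with a linked AE ending on Day 8: 8 − 3 + 1 = 6 days.

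The third example confirms that one reaction exists both as a diary event and as a linked unsolicited AE.

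**2. Following that fever through the tables.** It enters the Days 1–7 tables, the beyond-7-day tables and the count of events continuing past Day 7 (SAP 7.3.1). Its AE record carries the label unsolicited, so it also falls within all unsolicited TEAEs for Days 1–29 (SAP 7.3.2). The rule that counts a participant once per SOC or PT works within a table, not across the two sets.

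This does not depend on which start-date rule applies, because reaction onset and Day 8 both lie within Days 1–29. The duration of the AE record taken alone does depend on it: 8 − 3 + 1 = 6 days with the onset date, 8 − 8 + 1 = 1 day with a Day 8 start.

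**3. Possible size.** The documents give no event rates, so these inputs are assumptions: a proportion b with another unsolicited TEAE, a proportion p with a reaction past Day 7, and independence. The reported rate is 1 − (1 − b)(1 − p), so the increase is p(1 − b).

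| b | p | Reported rate | Increase (percentage points) |
|---|---|---|---|
| 10% | 1% | 10.9% | 0.9 |
| 10% | 5% | 14.5% | 4.5 |
| 10% | 10% | 19.0% | 9.0 |
| 20% | 1% | 20.8% | 0.8 |
| 20% | 5% | 24.0% | 4.0 |
| 20% | 10% | 28.0% | 8.0 |

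With the planned 100–150 participants per group, N × p runs from 100 × 0.01 = 1 to 150 × 0.10 = 15 participants appearing in both table sets.

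**4. Medically attended solicited reactions.** Taking the restrictive reading, the traces left by each kind of case are:

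| Solicited reaction with a medical visit | Where it still shows |
|---|---|
| Lasts past Day 7 | Its AE record can qualify as an MAAE |
| Inpatient hospitalization | SAE tables |
| ER visit | Grade 4 in the solicited severity tables, for most reactions (SAP Table 10) |
| 7 days or less, non-serious, outpatient visit | No table identifies it as medically attended |

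The severity grade does not fill the last row. For example, nausea or vomiting needing IV hydration outside hospital is Grade 3, the same grade as nausea that prevents daily activity. SAP 7.3.1 plans no table of medical attendance for solicited events.

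**The case against.** **On prolonged reactions.** The second AE entry is a deliberate protocol rule, no sentence orders a double count, and no planned table adds solicited and unsolicited counts together. All of that is right. It makes the defect a missing table rule rather than a wrong recording rule, but a programmer who follows the text would still include these records.

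**On the related rate.** A reader might infer that every linked record inflates the related column, because SAP 7.3.1 treats solicited events as related. The documents do not support this. That convention covers events reported within seven days of vaccination, and Protocol 8.1 and 8.1.1 require the investigator to assess causality for each AE record. The effect on the related rate depends on that assessment.

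**On immediate reactions.** Protocol 8.1.4.4 says "Any immediate reaction will be recorded as an AE on day of vaccination", and the diary starts the same day, so a reader might infer a second double count. No link between those AE entries and the diary is described. The post-vaccination observation is for immediate hypersensitivity (Protocol Table 1, footnote 8), which is not a diary item. This inference fails.

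**On MAAEs.** A reader might infer that the plan has settled on leaving out medically attended solicited reactions. It has not. The definition, the rule to report all MAAEs through Day 29, the endpoint and the table titles are unrestricted. The tables of MAAEs attributed to vaccine also carry no qualifier, and a medically attended solicited reaction could fit there. Only the qualifier in two sentences and the header point the other way. What stands is an internal conflict, with a narrow group of events affected on one reading.

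**Conclusion.** Both parts hold in limited form.

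First, as written, a diary reaction continuing past Day 7 is reported in the solicited tables and also counts in the unsolicited TEAE rate. The true size is unknown. The range of 0.8 to 9.0 percentage points rests wholly on the assumed 10–20% and 1–10% rates and on independence.

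Second, the MAAE analysis wording conflicts with the MAAE definition and secondary endpoint. On the restrictive reading, solicited reactions of 7 days or less with a non-serious outpatient visit are left out of the MAAE tables. Few such events are expected.

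A third, smaller inconsistency is the start date of the continuation record. The safety analyses are descriptive, with no test or decision rule on these rates. The primary immunogenicity analysis is untouched and the priority is low.

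**What to change.** - **SAP 7.3.2, TEAE tables.** Exclude AE records linked to a continuing diary reaction from the three tables of all unsolicited TEAEs. Report them in the beyond-7-day tables already planned in SAP 7.3.1. Keep them in the MAAE, AESI and SAE tables whenever they meet those definitions.
- **MAAE wording.** Delete the qualifier before MAAEs in SAP 7.3.2 and Protocol 9.3.3. Also change the header of the SAP table list, because otherwise the conflict remains. State that the MAAE tables count any AE meeting the Protocol 8.1.4.3 definition, solicited reactions included.
- **Start date.** Reconcile the rule in Protocol Table 1 footnote 9, Protocol 6.1.3 and SAP Table 7 footnote 9 (reaction onset) with Protocol 8.1.4.4 (Day 8).

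The cost is a few lines of wording and a filter on the link that the third duration method in SAP 7.3.1 already presumes. The downsides are that unsolicited rates may not compare directly with earlier sponsor tables that counted linked records, and that the MAAE count may rise slightly.

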7.4 Analysis of Exploratory Endpoints

The same statistical methods applied for the analysis of IgG, Nab, and hACE2 may also be applied to best characterize the immune response for future vaccine development needs, including testing against emerging variants of SARS-CoV-2 to evaluate immune responses developed based on the assays used as the exploratory endpoints.

